9.2 Laboratory

Hematology and blood chemistry data will be summarized separately by presenting descriptive statistics for baseline, post-baseline, and change from baseline values by lab parameter and visit. Shift tables (baseline to post-baseline values) based on normal range categories (low, normal, high, high & low) will be summarized separately for hematology and blood chemistry by lab parameter and visit.

Summaries of incidence of notable lab abnormalities for hematology and blood chemistry, reported from first dose of fingolimod among all studies, will present the number and percentage of patients with lab assessments satisfying notable criteria by visit. An overall study visit will be generated to indicate any notable abnormalities from post-baseline visits (including follow-up visits). Criteria for clinically notable laboratory values are specified in Appendix A. Percentages are based on the number of patients with non-missing lab result. A similar summary for patients with elevated liver function test values (elevation of 1, 2, 3, 5, 8 and 10 times the upper limit of normal) will be provided.

All summaries will be based on the fingolimod safety set.

Patients in the fingolimod safety set with notable post-baseline laboratory abnormalities will be listed separately for hematology and blood chemistry. All lab parameters with clinically notable criteria will be listed for a particular patient and visit if at least one of the parameters shows an abnormality. These listings will also indicate whether the lab result was above or below the normal range.

Patients with positive pregnancy test results during the long-term follow-up study part I will be listed for the safety set.

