#### **9.4.1.2 Laboratory**

Laboratory data collected up to the end of Study Part One will be summarized by presenting summary statistics of actual values and change from the first dose of fingolimod FDF baseline values and by presenting shift tables using clinically notable ranges (FDF baseline to most extreme post-baseline value). For liver function tests, the frequencies and percentages of patients with elevations of 1, 2, 3, 5, and 10 times upper limit of normal will be summarized by visit. [REDACTED]

A listing of laboratory data for patients with abnormal findings will be provided. In Study Part Two, only local laboratory test is performed for AE reporting purpose according to local policies and no laboratory data is reported in the clinical data base for analysis.

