### **Guidance on monitoring of patients with notable lymphopenia**

Fingolimod results in sequestration of a proportion of the circulating lymphocytes in lymph nodes with resultant reduction in circulating lymphocyte counts. Average circulating lymphocyte counts are expected to be around  $0.5-0.6 \times 10^9/L$  or  $500-600$  cells/ $\text{mm}^3$ . As such, the absolute total WBC, neutrophil and lymphocyte counts will be measured at each visit  $y$ . If the absolute lymphocyte count drops below  $0.2 \times 10^9/L$  or  $200$  cells/ $\text{mm}^3$  lymphocyte counts should be repeated regularly, at least monthly, and the patient should be reminded of the risk of infections and instructed to promptly report any symptoms of infections to the investigator. If monthly site visits create a logistical burden for the patient, local lymphocyte testing can be performed, with an eCRF comment added that lymphocyte counts were obtained locally and reviewed by the investigator. Study drug should be temporarily interrupted at the discretion of the investigator. Recovery of lymphocyte counts is expected to take approximately 1-2 months after stopping study drug given the long half-life of fingolimod. The patient should be evaluated and monitored for infections on a regular basis during this period.

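### SAP Part I replaces the protocol's baseline-to-worst shift table on notable laboratory limits with normal-range shifts by visit, so no planned table separates new from pre-existing notable values

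*SAP*

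**What the plan says.** Protocol 9.4.1.2 (Laboratory) commits to summarising laboratory data "by presenting shift tables using clinically notable ranges (FDF baseline to most extreme post-baseline value").

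SAP Part I 9.2 (Laboratory) specifies something else: shift tables from baseline to later values "based on normal range categories (low, normal, high, high & low"), which "will be summarized separately for hematology and blood chemistry by lab parameter and visit". It mentions no shift on notable limits and no shift to the most extreme value over the whole period.

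Notable values appear in SAP Part I 9.2 in two other places:

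- A summary of their incidence "will present the number and percentage of patients with lab assessments satisfying notable criteria by visit", with one further row: "An overall study visit will be generated to indicate any notable abnormalities from post-baseline visits (including follow-up visits"). The denominator is the number of patients with a non-missing result.
- Listings of patients who have a notable value after baseline.

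Neither is restricted to, or cross-classified by, notable status at FDF baseline. The SAP text gives no reason for departing from the protocol.

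The Part 2 SAP does not restore the table. Its laboratory section only lists positive pregnancy tests. This agrees with the protocol, which keeps Part Two laboratory results out of the clinical database.

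**The concern.** Long-term safety is the primary objective and the study has a single open-label arm. With no comparator, each patient's own value before fingolimod is the main reference for judging whether a laboratory abnormality arose on treatment. The protocol's table makes that comparison at the threshold chosen as notable. The SAP's tables do not. A normal-range shift uses baseline but cannot show who crossed the notable limit. The notable summary uses the limit but ignores baseline.

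An overall percentage headed as incidence would then combine two groups: patients who became notable after starting fingolimod and patients who were notable beforehand and stayed so or became so again. A reader of the study report could not separate them. The mixing matters most where a notable value may well exist before treatment. In SAP Appendix A the plausible candidates are cholesterol at 240 mg/dL or more and triglycerides at 300 mg/dL or more.

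**Working it through.** **Comparison of the two documents**

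| Feature | Protocol 9.4.1.2 shift table | SAP Part I 9.2 shift table | SAP Part I 9.2 notable summary |
|---|---|---|---|
| Categories | Notable limits | Normal range | Notable limits |
| Baseline cross-classified | Yes, FDF | Yes, FDF (default in SAP Part I 2.3.3) | No |
| Later value | Most extreme | Each visit | Each visit, plus any visit |
| Denominator | Not stated | Not stated | All patients with a result |

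The baseline is the same in both documents. The category and the time axis of the shift table have changed, and the baseline split at the notable limit appears in neither SAP table. The change-from-baseline statistics describe distributions, not threshold crossings. The liver table in multiples of the upper limit of normal is described as similar to the notable summary, with no condition on baseline.

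**Size**

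The documents state no figure on this point, so there is nothing to reproduce. The size has to be illustrated with assumed rates:

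- b: share of patients notable at FDF baseline, assumed 0-15%
- r: share of those who are notable again after baseline, assumed 50-90%
- i: rate of becoming notable among patients not notable at baseline, assumed 2-10%

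Formulas:

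- SAP overall percentage = b × r + (1 − b) × i
- Share pre-existing = b × r ÷ [b × r + (1 − b) × i]

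| b | r | i | Pre-existing, b × r | New, (1 − b) × i | SAP overall | Share pre-existing |
|---|---|---|---|---|---|---|
| 0% | any | 2% | 0% | 2.0% | 2.0% | 0% |
| 1% | 50% | 10% | 0.5% | 9.9% | 10.4% | 4.8% |
| 5% | 90% | 2% | 4.5% | 1.9% | 6.4% | 70.3% |
| 10% | 50% | 10% | 5.0% | 9.0% | 14.0% | 35.7% |
| 10% | 90% | 2% | 9.0% | 1.8% | 10.8% | 83.3% |
| 15% | 90% | 2% | 13.5% | 1.7% | 15.2% | 88.8% |

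In patients, using the estimated enrolment of about 5000 purely as a scale, the third row gives 5000 × 6.4% = 320 counted as notable. Of these, 5000 × 4.5% = 225 were already notable at baseline and 5000 × 1.9% = 95 are new.

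The denominators need care. In the fifth row the SAP table would show 10.8% of all patients. New cases are 1.8% of all patients, or 2.0% of those not notable at baseline. The like-for-like comparison is 10.8% with 1.8%.

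**The case against.** The strongest reply is that little is lost. Notable values are reported by visit and overall. Change from FDF baseline and normal-range shifts are planned. Clinically significant laboratory abnormalities are also captured as adverse events (Protocol 6.5.4 and 7.1). The analysis is descriptive, so no error rate or power is affected. All of this stands and limits the weight of the point. It does not supply the missing split: none of these outputs shows how many patients crossed a notable limit after starting fingolimod, and the adverse event route takes in only abnormalities that cause symptoms, need therapy or are judged clinically significant.

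Three stronger readings are tempting but unsupported:

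- *That severe lymphopenia goes unreported.* Lymphocytes below 0.2 × 10⁹/L are an Appendix A criterion and are counted by visit and overall. Protocol Appendix 5 says: "Average circulating lymphocyte counts are expected to be around" 0.5-0.6 × 10⁹/L on fingolimod. Values below 0.2 before the first dose are therefore probably rare, though this is an inference. If so, the overall row nearly equals the new-onset rate.
- *That a normal-range shift would put nearly every patient in normal-to-low for lymphocytes.* The documents give no lower limit of normal, and 0.5-0.6 is an average, so this cannot be derived.
- *That unscheduled or extreme values are left out of the SAP's shift tables.* The notes to Table 1 in SAP Part I 2.3.4 bring all individual assessments, including unscheduled ones, into shift tables and notable-value analyses. What is missing is the notable threshold and an overall baseline-to-most-extreme row.

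**Conclusion.** The point holds as a departure from the protocol with a bounded effect. SAP Part I omits a safety table that the protocol specifies, and no other planned table in either SAP supplies its information. The overall notable percentage counts patients already notable at FDF baseline as incident cases.

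The size depends on the parameter and cannot be fixed from the documents. It is nil where no patient is notable at baseline. Under the assumed ranges, pre-existing cases reach about 89% of the overall count when baseline abnormality is common and persistent and new onset is low. Many Appendix A parameters may lie near the lower end; cholesterol and triglycerides are the likelier exceptions. These placements are judgements, because no baseline prevalence is given.

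This should be corrected, because it changes how a primary safety result reads in a single-arm study. It does not mean that notable abnormalities go unreported.

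**What to change.** In SAP Part I 9.2, add the protocol's overall shift table for each Appendix A parameter: notable category at FDF baseline (low, none, high, or missing) by most extreme notable category after baseline. Use all scheduled and unscheduled assessments, as the notes to Table 1 in 2.3.4 already allow. Cover the same post-baseline period as the existing overall row, so that the totals reconcile.

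Beside the existing overall percentage, report new notable abnormalities as a number and as a percentage of patients not notable at FDF baseline. This second percentage goes beyond the protocol's wording, but it follows directly from the shift table. Keep the by-visit notable summary and the normal-range shifts as they are.

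If the sponsor prefers not to add the table, the SAP should record the change from Protocol 9.4.1.2 with a reason, and the notable summary should not be described as incidence.

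The cost is one additional table, plus a baseline notable-category flag if none exists. The baseline rule, the assessments and the limits are already specified.

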9.3 Routine vital signs

Vital signs include sitting pulse rate, sitting systolic and diastolic blood pressure, and oral temperature. Height and body weight were collected at the screening visit of the patient's previous fingolimod trial. First dose monitoring vital signs values will be excluded from routine vital signs summaries and listing.

Vital signs data will be summarized by presenting descriptive statistics for baseline, post-baseline, and change from baseline values by parameter and visit. The incidence of notable vital sign abnormalities reported from first dose of fingolimod among all studies will present the number and percentage of patients satisfying notable criteria by visit. An overall study visit will be generated to indicate any notable abnormalities from post-baseline visits (including follow-up visits). Criteria for clinically notable vital signs values are specified in Appendix B. Both summaries are based on the fingolimod safety set.

Patients in the fingolimod safety set with notable vital sign abnormalities will be listed. All vital sign parameters with clinically notable criteria will be listed for a particular patient and visit if at least one of the parameters shows an abnormality. The listing will also indicate whether the vital sign result was above or below the normal range.

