This analysis plan will describe the analyses which will be conducted on the CFTY720D series studies (from initial core/extension study to the long-term follow-up study) for Final CSR full analysis - long-term follow-up study part I. Patients participating in this study will provide clinical data of up to 15 years of exposure, which will provide information on the long-term safety, tolerability and efficacy profile of 0.5 mg fingolimod (FTY720) administered orally once daily in patients with relapsing forms of multiple sclerosis (MS) to help in therapeutic decision making. The full analysis will address safety updates for opportunistic infections and for basal cell carcinoma, since basal cell carcinoma has been reported in patients receiving fingolimod. Two follow-up visits (3-month and 6-month follow-up) are required after study completion to continuously monitor study safety.

Unless otherwise mentioned, all data collected from the first dose of fingolimod in the core/extension studies up to the end of the long-term follow-up study part I will be analyzed to evaluate the endpoints.

2 General strategies of data presentation

Statistical Analysis System (SAS) version 9.1 or higher will be used to perform all analyses.

In general, variables will be summarized using frequency distributions for categorical variables and summary statistics for continuous variables. Summary statistics for continuous variables will include n, mean, standard deviation, minimum, first quartile (Q1), median, third quartile (Q3) and maximum.

Note that, for CFTY720D2312 and CFTY720D2402 patients, the core study data is not included for any summary, and only information in the long-term follow-up study part I is included for listing purposes.

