2.3.3 Baseline and post-baseline

Unless otherwise specified, the baseline relative to the first dose of fingolimod (FDF) will be used throughout this study. It is defined as the last available measurement made prior to administration of the first dose of fingolimod among all studies a patient has participated in. The baseline can also be defined relative to the first dose of fingolimod during the long-term follow-up study in certain cases (i.e. ECG summary by visit), which is defined as the last available measurement made prior to administration of the first dose of fingolimod during the long-term follow-up study. The baseline relative to first dose of study drug in the core study (e.g. demographic information, core baseline characteristics) is also used for mentioned sections.

Post-baseline assessments are assessments made after the baseline assessment.

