 - Baseline will refer to the last value prior to the intake of the first dose of fingolimod. (Measurements labeled as "pre-dose" assessments will not be used as baseline values if the actual time variable suggests that the value has been obtained after the first dose of study medication: exceptions are body weight and temperature for which Day 1 records can be used as baseline irrespective of the actual time on day 1).
 - Multiple results per patient within a visit window will be averaged for summary statistics by considering both scheduled and unscheduled visits..
 - This visit windowing approach will only be used for summary statistics. (All individual assessments including unscheduled visits will be used to analyze notable and abnormal values, in shift tables and on listings.)
 - ** Week 2 for laboratory values will include day 1 post-baseline as the start day.

Table 2 Visit-windows for efficacy data (non-EDSS) domains

Visit	Start day (time)	Target Day (time)	End day (time)
Month 3	1	91	136
Month 6	137	182	273
Month 12	274	365	547
Month 24	548	730	912
Year 3 (M36)	913	1095	1278
Year 4 (M48)	1279	1461	1643
Year 5 M(60)	1644	1826	2008
Year 6 (M72)	2009	2191	2373
Year 7 (M84)	2374	2556	2739
Year8 (M96)	2740	2922	3104
Year 9	3105	3287	3469
Year 10	3470	3652	3834
Year 11	3835	4017	4200

...		every 12 months	
Month X (row i)	$S_i = \text{Integerpart}((D_i + D_{i-1}) / 2) + 1$	$D_i = \text{Integerpart}(X * 365.25 / 12)$	$E_i = \text{Integerpart}((D_{i+1} + D_i) / 2)$
...	...	Every 12 months	...
Month X (last row)	S_{last}	D_{last}	$E_{\text{last}} = D_{\text{last}} + (D_{\text{last}} - S_{\text{last}})$

- Day 1 is defined as the first dose day of fingolimod among all studies.
 - Baseline will refer to the last MRI value prior to Day 1.
 - For MRI: Visits 777 and 779 (study drug discontinuation assessments: the last scheduled scan is the reference scan), will be included in the visit windowing approach. However, 777 will only be used in a visit window if no other scheduled visit is available in the same window, if another scheduled visit is present, then the scheduled visit will take priority over 777.
 - If multiple assessments are available within a visit window, the record closest to the target day will be selected (if more than one assessment is at the same distance to the target day, the later one will be used for summary statistics (after unscheduled visits are excluded)).

Table 3 Visit-windows for EDSS efficacy data

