9.5 Dose monitoring administration

First-dose monitoring should be done on any patient who enrolls into this long-term follow-up study part I from any blinded study which has comparator treatment arms (placebo or active comparator, e.g. study CFTY720D2309) or enrolls from the comparator arm of an open-label controlled study or for any patient who has been off fingolimod treatment for the following durations:

- The treatment lasted for 14 days or less and was interrupted for 1 day or more, or
- The treatment lasted for more than 14 days and less than 29 days and was interrupted for more than 7 consecutive days, or
- The treatment lasted for 4 weeks or more and was interrupted for more than 14 consecutive days.

Patients requiring first dose monitoring should receive the first dose of fingolimod at the study center at a time which will allow for the required 6-hour post-dose monitoring to occur as well as to allow for additional time for extended monitoring, if necessary. The patient may be discharged if specific discharge criteria (refer to Protocol Appendix 4) are met. Hourly monitoring will be extended until findings have resolved if the discharge criteria are not met, and should pharmacologic intervention be required during first-dose observation, overnight monitoring in a medical facility should be instituted and the first-dose monitoring procedures should be repeated upon the 2nd dose.

A dose administration monitoring summary will be provided for the safety set for first/second/restart of fingolimod dose during the long-term follow-up study part I, and will include yes or no categorical summaries for the following: discharged at 6 hours, required extended monitoring after 6 hours, discharged but returned for monitoring, hospitalization, required Day 2 monitoring in the clinic (only recorded for first dose monitoring), study drug permanently discontinued, had symptomatic and/or treated bradycardia, and SAEs reported. The denominator for first/second dose monitoring data is based on the number of patients with assessment done; the denominator for restart monitoring data is based on the number of restarts.

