9.5.1 Vital signs

During the long-term follow-up study part I, hourly vital signs, including sitting pulse rate and blood pressure will be monitored before the first dose of fingolimod and every hour for at least six-hours thereafter.

Hourly dose monitoring of vital signs will be summarized separately and will not be included in the by-visit summaries of routine vital signs. Descriptive statistics of pre-dose, post-dose, and change from pre-dose values will be summarized by parameter and time point for first dose monitoring, second dose monitoring, and dose monitoring after study drug restart. Summaries will be based on the safety set and include dose monitoring data during the long-term follow-up study part I only.

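### First-dose pulse dips at hours 1-5 that recover by hour 6 are not counted as low pulses in any planned table unless symptomatic, treated or reported as an AE

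*SAP*

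**What the plan says.** The SAP document holds two plans, one for study part I and one for part 2.

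**Threshold count.** SAP Part I section 9.3 gives the number and percentage of patients meeting the Appendix B criteria, which for a low pulse are below 50 bpm or a fall of at least 15 bpm from baseline. The same section says: "First dose monitoring vital signs values will be excluded from routine vital signs summaries and listing".

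**Hourly pulses.** Section 9.5.1 says: "Descriptive statistics of pre-dose, post-dose, and change from pre-dose values will be summarized by parameter and time point for first dose monitoring", and does the same for second-dose and restart monitoring. Section 2 defines what that contains: "Summary statistics for continuous variables will include n, mean, standard deviation, minimum, first quartile (Q1), median, third quartile (Q3) and maximum". There is no per-patient lowest value, no count below a cut, and no listing of hourly pulses.

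**Other first-dose outputs.** The yes/no table in section 9.5 includes "required extended monitoring after 6 hours" and "had symptomatic and/or treated bradycardia, and SAEs reported". Section 9.5.2 summarizes monitoring ECGs, taken before dosing and at the end of the 6 hours.

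**Protocol.** Appendix 4 allows discharge at 6 hours if, among other conditions, the pulse is 45 bpm or more and is not the lowest hourly value. It also makes the lowest pre-dose reading the comparator. Section 9.4.1.3 plans the incidence of notable vital-sign abnormalities and does not exclude monitoring readings.

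**SAP Part 2.** Sections 9.3, 9.4 and 9.4.1 repeat this structure. Section 9.4.2 only lists the monitoring ECGs.

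**The concern.** Safety is the primary objective, and slowing of the heart after the first dose is a known effect of fingolimod. Protocol Appendix 4 says that the fall begins within an hour and is greatest within 6 hours, and that most patients with bradycardia had no symptoms. A low reading before hour 6 followed by recovery is the course that permits discharge on time. A bradycardia row restricted to symptomatic or treated cases can miss it.

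A reader of the study report would want to know how many monitored patients fell below a stated pulse. The plan gives a distribution at each hour instead. Patients reach their lowest pulse at different hours, so hourly distributions do not add up to a number of patients.

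**Working it through.** The plan states no sample size, power or error rate on this point, so there is no figure of its own to reproduce. The check traces one patient through the outputs and then tests whether the count can be rebuilt from the hourly statistics.

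**1. One patient (constructed).** Pre-dose pulse 68; hours 1-6: 62, 54, 46, 44, 52, 60.
- Falls: 6, 14, 22, 24, 16, 8.
- Below 50 bpm at hours 3 and 4; fall of 15 or more at hours 3, 4 and 5. The pulse is notable by Appendix B.
- Hour 6: 60 is at least 45, and the lowest value is 44 at hour 4. Both pulse discharge rules are met.

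Where this patient appears in SAP Part I:

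| Output | Counted as a low pulse? |
|---|---|
| 9.3 notable table and listing | No, first-dose values are excluded |
| 9.5 extended monitoring | No, pulse does not trigger it |
| 9.5 bradycardia row | Only if symptomatic or treated |
| 9.5.2 abnormal ECGs | No ECG is planned at hours 1-5 |
| 9.1 AE tables | Only if reported as an AE |
| 9.5.1 hourly statistics | One value in each hourly distribution; no patient count |

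**2. Can the count be rebuilt?** Take 100 monitored first doses, all with pre-dose pulse 65. At each of hours 1-5, five readings are 43 and ninety-five are 60. At hour 6 all are 62.

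Hourly statistics for each of hours 1-5:
- mean = (5 × 43 + 95 × 60)/100 = 59.15
- SD = √{[5 × (43 − 59.15)² + 95 × (60 − 59.15)²]/99} = √(1372.75/99) = 3.72
- minimum 43; first quartile, median, third quartile and maximum 60
- mean change = 59.15 − 65 = −5.85

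Hour 6: mean 62, SD 0, mean change −3. No pulse is below 45 at hour 6, and none is lowest there, since 62 exceeds every earlier reading.

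| Who is low | Ever <45 bpm | Ever <50 bpm | Fall ≥15 bpm | Mean lowest pulse |
|---|---|---|---|---|
| The same 5 at all five hours | 5 | 5 | 5 | (5 × 43 + 95 × 60)/100 = 59.15 |
| 5 at hours 1-2, another 5 at hours 3-5 | 10 | 10 | 10 | (10 × 43 + 90 × 60)/100 = 58.30 |
| A different 5 each hour | 25 | 25 | 25 | (25 × 43 + 75 × 60)/100 = 55.75 |

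Every planned hourly statistic is the same in all three rows. The mean of the per-patient lowest pulse separates them.

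**3. General bound.** With n_h patients below a cut at hour h out of N, the number ever below it lies between max(n_h) and min(N, Σn_h), here 5 to 25. The n_h are not planned outputs either.

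**4. Illustration of frequency, on assumed inputs.** Only the mean drop of 8 bpm comes from the documents (Appendix 4). Assume a pre-dose mean of 72 bpm, between-patient SD 8-12, SD of the drop 4-6, reading-to-reading SD 3-5, and 30%, 60%, 85%, 100%, 100% and 90% of the drop at hours 1 to 6. In simulation, the share with a notable reading at hours 1-5 that pass both pulse discharge rules and are not notable at hour 6 is 14-16% with reading SD 3 and 25-27% with reading SD 5. The share with a dip below 50 bpm and hour 6 at 50 or above, not notable, is about 4-6% and 8-10%. Much of the result depends on the assumed reading noise, so this is not an estimate for the trial.

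**The case against.** The plan follows the protocol's action rules. Appendix 4 treats the first-dose fall as transient and acts on symptoms, drug treatment, the pulse at 6 hours and ECG findings. Section 9.5 reports what follows from those. The hourly minimum also shows the most extreme reading at each hour. Keeping monitoring values out of a routine-visit table is sensible, and the fix keeps that rule. All of this stands, and it limits the point to a missing summary. It does not supply the number of patients.

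The 25-patient row needs isolated one-hour drops in different patients, which does not resemble the decline in Appendix 4. That is fair: the example proves that the count is not recoverable and says nothing about how often dips occur.

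Three stronger readings are tempting and are not supported:

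- **That first-dose bradycardia goes unreported.** Symptomatic or treated cases are counted, AE tables take cases judged clinically significant, and a pulse below 45 bpm or lowest at 6 hours leads to extended monitoring, which is counted for mixed reasons. Part I also counts abnormal 6-hour ECGs.
- **That second-dose and restart pulses leak into the routine table against an old baseline.** Section 2.3.4 says "All individual assessments including unscheduled visits will be used to analyze notable and abnormal values, in shift tables and on listings", and the default baseline in 2.3.3 is "the last available measurement made prior to administration of the first dose of fingolimod among all studies", which could be years earlier. But section 9.5 applies first-dose monitoring to restarts and repeats it at the second dose, and 9.5.1 keeps all hourly monitoring out of by-visit summaries. Only the listing is unclear.
- **That Part 2 has an equal gap.** SAP Part 2 section 2 leaves D2312 and D2402 patients out of every summary, and protocol Table 6-2 gives D2312 as its example of a blinded source study. Its first-dose tables would probably be nearly empty.

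One further objection changes the remedy. Monitoring covers all entrants from blinded controlled studies, including those already on fingolimod, so a single percentage would dilute the rate in true initiators.

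**Conclusion.** The point holds in this form. In SAP Part I, a first-dose pulse that becomes notable at hours 1-5 and has recovered by hour 6 is not counted as a low pulse unless it is symptomatic, treated or an AE, and the hourly statistics cannot supply the number. Recovered here means at least 45 bpm and not the lowest hourly value; otherwise extended monitoring picks the patient up.

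It is minor to moderate. The analysis is descriptive, no planned number is wrong, and only monitored doses are concerned. D2312 and D2402 patients are outside the point: SAP Part I section 2 says that "only information in the long-term follow-up study part I is included for listing purposes". How often such dips occur is unknown from the documents. That few first doses enter the Part 2 summaries is an inference from its exclusions, since no count is given.

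The conclusion assumes that the specific exclusion in section 9.3 overrides the general rule for notable values in section 2.3.4. That is the natural reading.

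**What to change.** **SAP Part I section 9.5.1**, beside the hourly statistics, add:
- each patient's lowest post-dose pulse during monitoring, and its change from the lowest pre-dose reading (the Appendix 4 comparator);
- n (%) with lowest pulse below 50 bpm (the existing notable cut), below 45 bpm (the existing discharge limit, used here only as a reporting cut) and with a fall of 15 bpm or more;
- a listing of those cases.

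Split first-dose results into true initiators and entrants already on fingolimod. The SAP already derives the first fingolimod dose across all studies, so this needs no new data. Show restarts separately, per restart.

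**SAP Part 2 section 9.4.1:** give the same counts for restarts and a listing for the rest.

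**Section 9.3 in both plans:** keep the routine-visit table separate, with a footnote that it and its listing exclude all dose-monitoring values, including second-dose and restart values.

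**Cost:** in Part I, one extra table and listing from readings already collected; in Part 2, a small restart table and a listing. A minimum over several readings includes some reading noise and will look lower than any hourly mean, so it should stand beside the hourly statistics and not replace them.
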